### Sample size

Based upon an effect size of 0.160 and a drop-out rate of 15%, a priori power analysis (G-Power Version 3.1.9.3) for mixed ANOVA suggested a total of 50 participants are required to detect SBP mean differences of at least 5 mmHg over time and groups ( $\alpha = 0.05$ ,  $1-\beta=0.80$ ). Despite this mean difference obtained from a study that characterized BP responses after acute isometric handgrip exercise (7), we also aim to examine the effects of training on acute blood pressure responses to isometric handgrip exercise. Thus, given these differences in study design, we additionally set the effect size considering the small, standardized effect sizes ( $\leq 0.20$ ) for exercise training sciences (31).

### Statistical analysis

Linear mixed models will be used to examine the effects of acute isometric handgrip exercise and training on BP, cardiac autonomic, and vascular function outcomes over time (i.e., aim 1, 2, and 3). These will be fitted with restricted maximum likelihood and applying Satterthwaite's method for approximating degrees of freedom for the F test using R lmerTest package (32). Fixed effects will be set as time, sex, training condition, and the random intercept as each participant. All models' residuals will be checked for normality and homogeneity of

variances using both Shapiro-Wilk and Levene tests, respectively, and through QQ plot inspection using the R performance package (33). Natural logarithm (Ln) transformations will be applied to HRV outcomes, as these are generally not normally distributed, but both transformed and untransformed data will be presented. Linear mixed models will be run with and without possible outliers identified through box plots as observations lying outside the 1.5 interquartile range. Unbiased effect sizes - partial omega squares ( $\omega^2$ ) will be estimated for each fixed effect and interactions terms and interpreted accordingly to the rough benchmarks set by Cohen (34) [small ( $\omega^2 < 0.05$ ), medium ( $\omega^2 < 0.25$ ), and large ( $\omega^2 > 0.25$ ) effects sizes]. Post-hoc comparisons will be performed using the Bonferroni correction, in the presence of significant fixed effects and interactions. MVC, %fat and free fat mass, and physical activity outcomes will be added to all linear mixed models as covariates, whereas resting HR and SRauc will be added to FMD and HRV main outcomes, respectively. In addition, the repeated measures correlation coefficient will be used to test associations between isometric handgrip exercise-induced BP changes before and after the training intervention and of BP with cardiac autonomic and vascular function outcomes (35). Multiple imputation procedures using full information maximum likelihood will only be used in case of a significant amount of missing data on outcomes (>15%) and if missing completely at random, as linear mixed modeling provides robust estimates for small to medium amounts of missingness (36). All statistical analyses will be conducted using R software, version 4.2.3 (37) with a significant level ( $\alpha$ ) of 0.05.

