## Sex Effects on Blood Pressure With Handgrip Training

### Research protocol

This study will be designed as a randomized, controlled, cross-over, repeated measures experiment. Fifty young healthy adult participants (25 males and 25 females) will visit the laboratory three times to perform a fatiguing bout of isometric handgrip exercise before and after both 4 weeks of isometric handgrip training and a no-exercise training condition. Participants will be randomly allocated to the isometric handgrip and the non-exercise training conditions using an online program (<http://www.randomizer.org/>). Participants that start with isometric handgrip training will return to the laboratory after a 4-wk washout, as this duration has been shown to decondition cardiovascular outcomes following training (1–3). To eliminate diurnal variation, each participant will visit the laboratory at the same time of day. Main outcomes in each visit will be measured at rest, during the fatiguing bout of isometric handgrip exercise, and 5, 10, 30, and 60-min post-exercise (see figure and Table 1). These measurement timings are aimed to characterize BP, and the cardiac autonomic and vascular function biphasic responses (4–6). Visits 2 and 3 will take place within 7 days of the last training session.

**Figure 1:** Experimental design, a randomized, controlled, cross-over, repeated measurements study. Abbreviations: CON; control, BRS baroreflex sensitivity, RMSSD, root mean square of

**Table 1** Procedures to be conducted in each visit to the laboratory

Procedures	Time (min)
Rest	15
Measurements	
1) BP, arterial stiffness, cardiac autonomic function	5
2) Brachial endothelial function (FMD)	15
Fatiguing isometric handgrip exercise	~ 3-5
Last isometric contraction	
Measurements	
1) BP, brachial blood flow	
2) Cardiac autonomic function (BRS, RMSSD, HF)	
Post 5 min	
Measurements	
1) BP, arterial stiffness (cfPWV), cardiac autonomic function (BRS, RMSSD, HF)	5
Post 10 min	
Measurements	
1) Brachial endothelial function (FMD)	15
Post 30 min	
Measurements	
1) BP, arterial stiffness (cfPWV), cardiac autonomic function (BRS, RMSSD, HF)	5
2) Brachial endothelial function (FMD)	15
Post 60 min	
Measurements	
1) BP, arterial stiffness (cfPWV), cardiac autonomic function	5
2) Brachial endothelial function (FMD)	15
	Total ~ 100

successive differences; HF, high-frequency power band; FMD; brachial artery flow-mediated dilation, cfPWV; central pulse wave velocity.

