#### Isometric handgrip training intervention and control

Participants will train three days per week at home for 1 month using a reliable and validated digital handgrip dynamometer (DynX, MD System, Inc., Westerville, OH, USA)) in a seated position. The isometric handgrip training protocol will consist of four sets (2 for each hand) of two-min sustained contractions starting at 30% MVC interspersed by 1-min resting periods (a total of 12-min). All training sessions will be remotely supervised via Zoom or phone call by a research team member to ensure compliance with the exercise prescription. Before each training session, MVCs will be re-assessed over three repetitions, each separated by 30-s, to ensure an accurate exercise prescription (13). The highest value will be used to determine the target intensity of the session. In the control/washout conditions, participants will be instructed to maintain their normal daily routines.

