#### Post-intervention visits – isometric handgrip exercise acute bout

All participants will return to laboratory to complete the same acute bout of isometric handgrip exercise detailed in the baseline visit after the isometric handgrip exercise training and respective control.

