## Procedures involved

### Study assessment procedures

#### Cardiovascular function

During the study visits, all non-invasive cardiovascular function measurements detailed below will be done in a quiet climate-controlled room (22-24° C) after a 15-min resting period, during, and after the fatiguing handgrip exercise with participants in a supine position. Participants will be tested in a fasted state (4h) and have refrained from exercise, caffeine/alcohol intake, and vitamins/supplements in the last 24h. Cardiovascular function testing in females will occur without controlling for the menstrual cycle (33,34), given that a growing body of literature supports little to no variation in BP, cardiac autonomic (i.e., BRS), and vascular function outcomes (i.e., brachial artery FMD and cfPWV) at rest and during acute exercise across the menstrual cycle or oral contraceptive pill cycle (25,27–32).

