### *Vascular function*

During the vascular function measurements, we will ask participants to lie quietly in the supine position. They will also experience a forearm occlusion to permit the assessment of endothelial function.

**Endothelial function:** will be non-invasively assessed via brachial artery FMD, which represents nitric oxide-dependent vasodilation and closely correlates with the endothelial function of the coronary arteries (20,21). FMD will be assessed in the right brachial artery with an ultrasound (Arietta V750, Fujifilm, Tokyo, Japan) equipped with a 7.5-MHz linear array probe incorporating a 5-MHz Doppler transducer, placed  $\sim 4$  cm above the antecubital fossa, and held by a stereotactic clamp following standard guidelines (22,23). Reactive hyperemia will be induced by rapid cuff deflation following a forearm occlusion (Hokanson SC10, Bellevue, WA 98005, USA) maintained for 5-min at 250 mmHg. Changes in intraluminal brachial artery diameter will be tracked with automated edge-detection software (FMD studio, Quipu srl, Pisa, Italy) allowing precise measurement of the artery diameter (23). Doppler measurements of peak hyperemic blood velocity with an insonation angle of  $\leq 60^\circ$  will allow calculation of FMD main stimuli - shear rate as  $(4 \times \text{peak blood velocity} / D_{\text{baseline}})$  (23). All FMD analyses will be done offline using the FMD studio. FMD will be presented both as an absolute change ( $\text{FMD (mm)} = D_{\text{peak}} - D_{\text{baseline}}$ ) and as a relative change ( $\% \text{ FMD} = (D_{\text{peak}} - D_{\text{bas}}/D_{\text{baseline}}) \times 100$ ) in diameter. If a non-linear ratio between  $D_{\text{peak}}$  and  $D_{\text{bas}}$

is observed (B coefficients < 1), %FMD will be allometrically scaled for  $D_{baseline}$  (24,25). In addition, blood flow will be estimated as (Mean blood velocity) x (Brachial Cross-Sectional Area) x (60). Brachial artery blood flow will be measured in both exercising and non-exercising arms. All FMD scans will be conducted by the same researcher with inter-day measurements CV <15% (22,23).

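### Every visit includes the handgrip bout, so the post-exercise time main effect cannot be read as the effect of acute exercise; the training and sex contrasts keep their comparators

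*Combined protocol and SAP*

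**What the plan says.** The Statistical analysis section names acute exercise as a target of inference alongside training: "Linear mixed models will be used to examine the effects of acute isometric handgrip exercise and training on BP". The fixed effects are time, sex and training condition, with a random intercept per participant. No factor distinguishes a session with the bout from one without it.

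Under Research protocol, participants "will visit the laboratory three times to perform a fatiguing bout of isometric handgrip exercise". Main outcomes are "measured at rest, during the fatiguing bout of isometric handgrip exercise, and 5, 10, 30, and 60-min post-exercise". The section on post-intervention visits adds: "All participants will return to laboratory to complete the same acute bout of isometric handgrip exercise detailed in the baseline visit". This applies after training and after control alike. The control is defined by what happens between visits: "In the control/washout conditions, participants will be instructed to maintain their normal daily routines".

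The Cardiovascular function section has measurements taken before, during and after "handgrip exercise with participants in a supine position". Table 1 schedules FMD at rest and at 10, 30 and 60 min after exercise. The Vascular function section describes each FMD test as a forearm occlusion "maintained for 5-min at 250 mmHg".

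**The concern.** The word control invites the assumption that both parts of the aim have a comparator. Only training has one. For acute exercise, the only model term that can carry an average effect is time within visit, and that is a before-after comparison. Lying supine, repeated cuff occlusions and the bout all lie between the resting reading and the later ones, and nothing in the design separates them.

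If the plan is followed as written, an average change in BP, autonomic indices, FMD or carotid-femoral pulse wave velocity at 30 or 60 min would be reported as an effect of handgrip exercise, although rest and the test procedures could have produced some or all of it.

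**Working it through.** The plan gives no figure for within-session drift, so there is none to reproduce. The check is a count from Table 1, followed by a look at which contrasts are affected.

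**Inputs.** From Table 1: resting BP, stiffness and autonomic block 5 min; FMD 15 min; bout about 3-5 min; BP at the last contraction and at 5, 30 and 60 min; FMD at rest, 10, 30 and 60 min, with BP before FMD at rest, 30 and 60 min. From Vascular function: one 5-min occlusion per FMD.

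**Elapsed time and earlier occlusions.** Time is counted from the start of resting BP, using Table 1 durations only: 5 + 15 + (3 to 5) + minutes after exercise.

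| Reading | Elapsed time (min) | Occlusions already done |
|---|---|---|
| BP at last contraction | 5 + 15 + 3 to 5 = 23-25 | 1 (rest) |
| BP at 5 min | 23-25 + 5 = 28-30 | 1 (rest) |
| FMD at 10 min | 23-25 + 10 = 33-35 | 1 (rest) |
| BP at 30 min | 23-25 + 30 = 53-55 | 2 (rest, 10) |
| BP at 60 min | 23-25 + 60 = 83-85 | 3 (rest, 10, 30) |

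A fourth occlusion follows the 60-min BP. Exposure is therefore uneven: the end-of-contraction and 5-min readings follow only the resting occlusion, while the 30- and 60-min readings carry most of the burden.

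**What each contrast estimates.** Write the mean change from rest at a given time as E + D, where E is the effect of the bout and D is the drift from rest and procedures. Use T and C for trained and control visits, F and M for females and males.

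- Time main effect: E + D. No session has D alone, so E is not identified.
- Training-by-time: (E_T + D) − (E_C + D) = E_T − E_C, if D is the same at both visits.
- Sex-by-training-by-time: (E_TF − E_CF) − (E_TM − E_CM), under the same condition within each sex.
- Time-by-sex: (E_F − E_M) + (D_F − D_M). The second term is zero if drift does not differ by sex.
- Trained versus control at rest: contains neither E nor D, because it is measured before the bout and before any occlusion in that visit.

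**Illustration only.** Drift and standard deviation are both assumed here. Take 42 completers (50 × 0.85 = 42.5, rounded down), no true bout effect, and a two-sided paired test of rest against 60 min at 0.05. A drift of 2 mmHg would be significant with probability 0.24, 0.35 or 0.56 at a standard deviation of change of 10, 8 or 6 mmHg; a drift of 3 mmHg with probability 0.48, 0.66 or 0.89. This shows that a trial of this size could declare a modest drift significant. It does not show that such a drift exists.

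**The case against.** The strongest reply is that the plan's main interest lies elsewhere. The title concerns sex, and the Sample size section states an aim to examine how training alters acute BP responses; both have comparators. The Statistical analysis section does not assign an interpretation to each model term, and the text of aims 1 to 3 is not in the documents. The 15-min rest before the first reading should also reduce early settling. All of this narrows the point. It does not remove it: the section still names the effects of acute exercise as a target and later speaks of BP changes induced by the exercise, and only the time term can carry such an average effect.

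Blood flow is measured in the non-exercising arm as well, but that is a local reference for flow. It does not serve BP, autonomic function, FMD or pulse wave velocity.

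A reader might infer four stronger things that the documents do not support:

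- That time-by-sex is compromised to the same degree. It is not: drift shared by males and females cancels, and nothing in the documents points to sex-specific drift.
- That only training-by-time contrasts can bear a causal statement. That would wrongly exclude the trained-versus-control difference at rest, which within-session drift cannot reach.
- That all the late readings follow an hour or more of supine time. Counted from resting BP, this holds at 60 min (83-85 min) but not at 30 min (53-55 min).
- That the bias can be sized. A drift of 1-4 mmHg would be 1/5 to 4/5, or 20-80%, of the 5 mmHg in the Sample size section, but that drift range is an assumption with nothing behind it in the documents.

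The plan also does not commit itself to concluding post-exercise hypotension; that term appears only in the titles of cited papers.

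**Conclusion.** The point holds for the post-exercise time main effect, chiefly at 30 and 60 min. There the design cannot separate the bout from about 53-55 or 83-85 min of elapsed time and two or three earlier occlusions. The size and direction of any bias are unknown. This conclusion is structural and does not depend on the illustration above. The elapsed times assume that Table 1's steps follow one another without gaps; extra time, for example for the maximal-contraction attempts, would lengthen them.

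The training contrasts stand if drift is equal across visits, and time-by-sex stands if drift does not differ by sex. The resting contrast is unaffected by this problem. The end-of-contraction reading is the least exposed measure of the exercise response, though it too follows the resting occlusion. One stated target is not identified as written; the trial's training and sex questions survive.

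**What to change.** In the Statistical analysis section and in the report:

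1. Describe the post-exercise time main effects as uncontrolled within-session change after the bout and test procedures, not as the effect of acute exercise. Say that exposure builds from the 10-min scan onward and is greatest at 30 and 60 min.
2. Draw causal training conclusions from the training-condition contrasts, both at rest and training-by-time, including their interactions with sex. State the assumption of equal drift across visits for the training-by-time contrasts.
3. Report time-by-sex as a sex difference in the post-bout response, valid if drift from rest and procedures does not differ by sex.
4. Keep the end-of-contraction reading as the least exposed measure of the exercise response, and note the resting occlusion before it.

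This changes wording only, with no added visit, measurement or participant. The downside is a weaker claim for the acute-exercise aim. Recovering the stronger claim would need a session with the same posture and test schedule but no bout, which is a larger change and is not required for the rest of the plan to stand.

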## Study intervention

### Baseline visit – fatiguing bout of Isometric handgrip exercise

All participants will rest for 15-min, and then the MVC will be determined based on three attempts, each separated by 30-s, with participants in a supine position. The highest MVC will be used to define the exercise workload (30% MVC). Then, participants will perform a fatiguing bout of unilateral isometric handgrip exercise in the supine position using a digital handgrip transducer intertwined with a data acquisition system (Powerlab 16/35; ADInstruments, BellaVista, NSW, Australia). Participants will use their dominant hand and will hold the isometric contraction until task failure. The failure criteria will be defined as the inability to sustain the contraction force within 5% of the target MCV percentage (i.e., 30%). We chose to set the intensity at 30% MVC as this is the standard target intensity of isometric handgrip exercise protocols (7–9) and no differential BP responses have been reported when different intensities (i.e., 20 vs 30 and 45% MVC) are

used (10–12). Based on previous research, we expect that participants will fatigue within 3 to 5 min (i.e., time to task failure) (12). Participants will receive both visual and auditory feedback to maintain the target exercise intensity throughout the session. The same fatiguing bout protocol will be used before and after the training intervention.

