### *Cardiac autonomic function*

We will place electrodes directly on the skin of each participant to obtain the ECG trace required to estimate both heart-rate variability and baroreflex sensitivity outcomes.

**Heart rate variability and baroreflex sensitivity:** R-R intervals will be sampled at 1000 Hz frequency to obtain digital R waves digital sequences using the single ECG lead module of PowerLab data acquisition system (ADInstruments, BellaVista, NSW, Australia). All data acquisition and offline analyses will be conducted following the standards of the Task Force of the European Society of Cardiology and the North American Society of Pacing and Electrophysiology (17). Offline heart rate variability (HRV) analyses will be performed over a 2-min time series for each time-point (i.e., baseline, during and 5, 30 and 60 min after exercise) using the HRV analysis module of Lab Chart 8 (ADInstruments, BellaVista, NSW, Australia) (18). Main time-domain indices of interest include the standard deviation of NN intervals (SDNN) – a measure of overall variability, and the root mean square of the sum of the squares of the differences between NN intervals (RMSSD) – a measure of cardiovagal modulation. In addition, non-linear time-domain parameters will be derived from the Poincaré plot, including the vertical deviation that reflects mainly cardiovagal modulation (SD1), the longitudinal deviation (SD2), and the non-linear ratio SD1/SD2 an index of autonomic balance analogous to LF/HF ratio (19). The time-frequency domain analysis will be conducted using the Lomb-Scargle Periodogram, which permits accurate estimation of low (0.04 to 0.15 Hz) and high-power frequency (HF) power bands (0.15 to 0.40 Hz) in absolute and normalized power units during exercise conditions. Cardiac baroreflex sensitivity (BRS) will be estimated via the spontaneous sequence method over 2 min through the Lab Chart 8 baroreflex macro. Briefly, this method identifies ramps where increases in SBP ( $> 1$  mmHg) are coupled with increases of the RR interval ( $> 4$  ms) (linearly correlated) that occur over at least 3 beats (minimum sequence). The minimum acceptable correlation coefficient between SBP and RR interval ramps will be 0.80. Then, baroreflex sensitivity is estimated as the average of all regression slopes between the SBP and RR interval.

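### The mixed model has no visit-within-participant term, so training and sex-by-training are tested against an error that leaves out most of the visit-to-visit variation

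*Combined protocol and SAP*

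**What the plan says.** All references are to the combined protocol and SAP.

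- **Model.** Statistical analysis states "Fixed effects will be set as time, sex, training condition, and the random intercept as each participant". The models are "fitted with restricted maximum likelihood and applying Satterthwaite's method for approximating degrees of freedom". No visit or condition-within-participant term, random slope or residual correlation structure appears anywhere. Interaction terms are mentioned but not listed.
- **Design.** Under Research protocol, participants "will visit the laboratory three times to perform a fatiguing bout of isometric handgrip exercise": at baseline, after training and after control. Each visit belongs wholly to one condition.
- **Readings per visit.** Heart rate variability and baroreflex sensitivity are taken at "baseline, during and 5, 30 and 60 min after exercise", which is five times. Table 1 gives the same five for blood pressure. It gives four for FMD (rest, 10, 30, 60 min) and four for cfPWV (rest, 5, 30, 60 min). Cuff pressure, taken only before and after exercise, also has four.
- **Questions.** The title is "Sex Effects on Blood Pressure With Handgrip Training", which points to sex-by-training. The Sample size section adds "we also aim to examine the effects of training on acute blood pressure responses to isometric handgrip exercise", which is training-by-time. The documents do not rank the two.

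**The concern.** This is a split-plot layout: visits are the whole plots, readings within a visit are the subplots, and training is a whole-plot factor. Training and sex-by-training should be judged against variation between visits of the same participant. With a participant intercept alone, that variation is pooled into a residual made up mostly of within-visit noise. Satterthwaite's method does not repair this, because it approximates degrees of freedom for the model as specified. Nor do the planned normality and equal-variance checks detect clustering within visits.

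The visit-level variance is not reported, but the documents suggest it is above zero:

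- Vascular function: "All FMD scans will be conducted by the same researcher with inter-day measurements CV <15" percent. This allows day-to-day variation, although it is not split into day and within-day parts.
- Baseline visit: "Participants will use their dominant hand and will hold the isometric contraction until task failure". Exercise duration can therefore differ from visit to visit.
- The section on individual responsiveness looks for differences in training response between participants. If they exist, they are participant-by-condition variance, which the model omits.

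Testing at the same time of day, fasted and in a controlled room limits this variance but does not remove it. At stake is a sex-by-training or training effect declared from chance visit-to-visit shifts and, in the same model, a real training-by-time effect missed.

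**Working it through.** **The plan's own figure.** The plan states no degrees of freedom or standard error for these tests. Its one related number is 50 participants (f = 0.160, α = 0.05, power 0.80, 15% dropout). The number of measurements m and the correlation ρ are not stated. Assuming m = 6 and ρ = 0.5, with λ = f²Nm/(1−ρ), gives N = 43, and 43 × 1.15 = 49.5, or 50. The figure is reachable but does not bear on this point, except that 50 × 0.85 = 42.5, taken as n = 42 completers.

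**Inputs.** From the documents: n = 42 in two sexes, T = 4 or 5 readings per visit, and C = 3 visits (or 2 if only the post-condition visits are modelled). Assumed, because the documents are silent:

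- share = visit-level variance / (visit-level + within-visit residual variance), 0 to 0.50; r = share/(1 − share)
- q = participant-by-time variance / within-visit residual variance, 0 to 1

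**Degrees of freedom.** Planned model: (n − 2)(CT − 1). With a visit term: (n − 2)(C − 1).

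| C | T | Planned | With visit term |
|---|---|---|---|
| 2 | 4 | 40 × 7 = 280 | 40 |
| 2 | 5 | 40 × 9 = 360 | 40 |
| 3 | 4 | 40 × 11 = 440 | 80 |
| 3 | 5 | 40 × 14 = 560 | 80 |

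Alone, this changes little: the critical t is 1.96-1.97 instead of 1.99-2.02. The standard error does the harm.

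**Standard error.** In a balanced design,

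(true SE / model SE)² = (1 + Tr) / {[(1 + Tr)d_pc + (1 + Cq)d_pt + d_pct] / d_res}

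Here d_pc, d_pt and d_pct are the participant-by-condition, participant-by-time and three-way degrees of freedom, which sum to d_res.

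Worked case: C = 2, T = 4, share 0.20. Then r = 0.20/0.80 = 0.25, 1 + Tr = 2, d_pc = 40, d_pt = 120, d_pct = 120 and d_res = 280.

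- q = 0: denominator (80 + 120 + 120)/280 = 1.143; ratio √(2/1.143) = 1.32
- q = 0.3: (80 + 1.6 × 120 + 120)/280 = 1.40; ratio √(2/1.40) = 1.20
- q = 1: (80 + 3 × 120 + 120)/280 = 2.00; ratio 1.00

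Over all four C and T combinations at share 0.20, the ratio is 1.30-1.41 (q = 0), 1.18-1.27 (q = 0.3) and 1.00-1.05 (q = 1). It equals 1 at r = q/T. The standard error is therefore too small exactly when visit-level variance exceeds one quarter (T = 4) or one fifth (T = 5) of the participant-by-time variance.

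**Type I error for training at nominal 5%**, simulated from the mean squares (sex-by-training agrees within simulation error):

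| share | q = 0 | q = 0.3 | q = 1 |
|---|---|---|---|
| 0.05 | 7-9% | 4-5% | 1-2% |
| 0.10 | 9-12% | 6-8% | 2-3% |
| 0.20 | 14-21% | 10-15% | 5-7% |
| 0.50 | 27-42% | 24-37% | 17-28% |

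At share 0 and q = 0 it is 5%.

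**Training-by-time.** Type I error is 0-5% in every cell. At share 0.20, an effect with 80% power under the correct error term has 69-75% (q = 0) or 50-63% (q = 0.3) under the planned model.

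**REML fits to simulated data.**

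- C = 2, T = 5, share 0.20, q = 0 (150 data sets): mean model SE 0.093 against an empirical SD of 0.131, ratio 0.71, with 15% rejection.
- C = 2, T = 4, share 0.20, q = 0.3 (200 runs, some convergence warnings): 9.0% for training and 10.5% for sex-by-training under the planned model; 6.0% and 5.5% with both terms proposed below.

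**The case against.** The missing term is plain from the text. The case on the other side is about how much it matters.

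- **Size unknown.** Neither variance is in the documents, and the table runs from 1-2% to 42%. At q = 1 the test is conservative or close to nominal up to share 0.20. This stands, and the conclusion is conditional on it.
- **Thin evidence.** The FMD limit concerns operator reliability for one outcome. Holding to task failure cannot shift the resting reading, so it acts only partly as a shift shared by the whole visit. Looking for individual response does not show that it exists. All fair: the evidence supports a variance above zero, not a value.
- **Covariates.** MVC, physical activity and, for some outcomes, resting heart rate or shear rate enter the models. If entered per visit, which the plan does not say, they may absorb part of the visit-level variance. They do not replace the error term, and the calculation does not model them.
- **Which tests.** Inflation affects effects averaged over the readings of a visit. A training contrast at a single time point, at share 0.20, gives 5.8-6.2% (q = 0), 3.7-4.5% (q = 0.3) or about 1% (q = 1). Sex-by-training is implied by the title and the mention of interactions, not named as a time-averaged test.
- **Equal variances.** The finding that training-by-time is conservative depends on them. With four-fold variance at one time point and neither visit nor participant-by-time variance, its type I error is 6.3-7.5%.
- **REML precision.** In the 200-run check, 9.0% has a 95% interval of 5.4-13.9%, which overlaps that for 6.0% (3.1-10.2%). The conclusion rests on the mean-square results, not on that run.

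None of this supplies the missing error term. A confirmatory analysis should not depend on an unreported variance being negligible.

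**Conclusion.** The concern holds and should be corrected before analysis. The gap in degrees of freedom, 280-560 against 40-80, follows from the design with 42 completers, two or three visit levels and four or five readings. The standard error for training and sex-by-training is too small whenever visit-level variance exceeds 1/T of the participant-by-time variance. How far that goes cannot be settled from the documents. Across the assumed ranges, the planned test runs from valid or conservative to several times its nominal error.

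Under equal variances, training-by-time is conservative and loses power. The direction of error for the main time test is not established. The calculations assume balanced data and no covariates. Outcomes analysed with a single value per visit are not affected.

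**What to change.** In Statistical analysis, add a random intercept for visit within participant: `(1|id) + (1|id:visit)`, or an equivalent such as a random training effect per participant. Preferably add `(1|id:time)` too. With the visit term alone and q = 0.3, the main time test remains at 9-18% and training-by-time at 1-2%.

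Keep REML and Satterthwaite. Also state:

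- that each term stays in the model if its variance is estimated as zero;
- whether training condition has two levels or three;
- which interactions are tested.

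With variances truncated at zero, the visit term holds training type I error to at most 5.2% in every cell examined. Adding the participant-by-time term gives 4.1-6.2% for training, time and training-by-time.

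The cost is one or two terms in the model formula and no new data. P-values for training and sex-by-training become less favourable if visit-level variance is present. Some fits may be singular, and Satterthwaite degrees of freedom move back towards the residual value where the visit variance is estimated as zero. The change should be made before results are seen, because an error term chosen afterwards would be open to challenge.
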